11.1 Clinical assessments

11.1.1 Medical history

The medical history will include any conditions reported by the subject or noted by the investigator in each body system, including allergies or drug sensitivities, past surgeries and any history of substance abuse (drug or alcohol), and will be recorded at screening. A review of the subject's medication use will also occur.

A migraine history, to include frequency, duration and severity of headaches, will be recorded. Sufficient information should be collected to confirm the diagnosis, ie intensity, throbbing/nonthrobbing, aggravating factors, aura, unilateral or bilateral, associated symptoms, eg photophobia, phonophobia, nausea, vomiting, cognitive impairment, dizziness, functional disability, most troublesome symptom.

11.1.2 Demographics

Demographic information will include the subject's age, gender and ethnic affiliation.

11.1.3 Electrocardiogram

12-lead ECGs will be performed with subjects lying in a supine or semi-supine position for at least 5 minutes prior to measurement. All ECG tracings will be reviewed by the Investigator or an appropriately medically qualified reviewer designated this responsibility by the Investigator.

Any subject with an abnormal ECG at screening that is considered clinically significant will be excluded from the study.

11.1.4 Vital signs

Resting supine or semi-supine blood pressure (systolic and diastolic), heart rate, and respiratory rate will be evaluated. The same arm should be used throughout the study. Body temperature (tympenic), will also be evaluated as part of vital signs.

Subjects should be resting in a supine or semi-supine position for at least 5 minutes prior to and during vital signs measurement.

11.1.5 Physical examination

Physical examinations are to be performed by a medically qualified physician according to their standard medical practice. Any new or worsening abnormality, clinical sign or finding must be documented.

A full physical examination is to be performed at the first screening visit. At other scheduled time points, a targeted (symptom directed) physical examination, as clinically indicated, is to be performed.

A full physical examination will include assessments of the head (eyes, ears, nose, mouth, throat), skin, neurological system, respiratory system, cardiovascular system, musculoskeletal system, abdomen (liver and spleen), lymph nodes and extremities, general appearance, and any additional assessments needed to establish baseline status or change from baseline or evaluate symptoms or adverse events.

11.1.6 Height and weight

Height (centimetres) and weight (kilogram), without shoes, will be measured and BMI calculated.

11.2 Laboratory assessments

11.2.1 Clinical safety testing

Blood samples will be tested at one nominated laboratory per study site. Urinalysis (dipstick) will be performed at the investigational site.

Details of the volume of blood and type of tubes required for the following tests will be provided in the Study Manual. At the investigator's discretion, sample collection may be repeated if an abnormal result occurs due to technical or other reasons.

The following tests will be performed.

11.2.1.1 Haematology

Haemoglobin, haematocrit, red blood cell count, white blood cell count with differential (neutrophils, lymphocytes, monocytes, basophils, eosinophils), platelet count, mean corpuscular haemoglobin, mean corpuscular volume, mean corpuscular haemoglobin concentration

11.2.1.2 Clinical chemistry

Glucose, sodium, potassium, chloride, bicarbonate, calcium (corrected), creatinine, urea, uric acid, amylase, lipase, triglyceride, HDL-cholesterol, LDL-cholesterol, total cholesterol, total protein, lactate dehydrogenase, creatine kinase, C-reactive protein, albumin, phosphate

11.2.1.3 Liver function tests

Aspartate aminotransferase, alanine aminotransferase, gamma-glutamyl transferase, alkaline phosphatase, conjugated bilirubin, total bilirubin

11.2.1.4 Coagulation

Activated partial thromboplastin time, international normalised ratio

11.2.1.5 Urinalysis

Specific gravity, pH, glucose, protein, blood, ketones, urobilinogen, bilirubin, nitrite, leukocytes.

If urinalysis on dipstick is positive for leukocytes and/or blood/haemoglobin, a microscopic examination including erythrocytes, leucocytes, bacteria, casts, epithelial cells and crystals will be performed.

11.2.2 Pregnancy

Human chorionic gonadotropin levels (hCG) will be measured in blood samples from females of child-bearing potential at screening. Urine hCG will be measured at other time points.

11.3 Adverse event monitoring

Subjects will be asked by direct questioning at each visit whether they have experienced any AEs. AEs will be assessed as described in Section 13.2.

11.4 Concomitant medications

Changes in use or new medications used during course of study will be documented and reviewed at each study visit.

11.5 Efficacy assessments

11.5.1 Pain intensity

Migraine pain intensity will be recorded using the NRS in a subject migraine diary at the start of dosing (t

= 0 min) and at 0.5, 1.0, 1.5, 2, 4, 8 and 24 hours post dose. The NRS is an 11-point scale which grades pain from 0 (no pain) to 10 (worst pain imaginable). Pain should reflect the subject's pain at the time of recording.

11.5.2 Migraine symptoms

Each subject will specify his/her most troublesome symptom at baseline (Day 1).

On the day of a migraine headache, baseline information about the headache should be recorded to verify that the headache was an acute migraine headache including headache intensity, aura, presence or absence of associated symptoms, unilaterality or bilaterality of the headache, aggravation by exercise, throbbing or nonthrobbing.

The subject's symptoms will be recorded on an 11-point Likert scale. This scale allows the subject to record the presence of the symptom from 0 = no symptoms to 10 being severe symptoms. Symptom assessments will be recorded in the subject's diary prior to dosing (t = 0 min) and at 0.5, 1, 1.5, 2, 4, 8 and 24 hours post dose. Symptoms to be recorded include nausea, photophobia and phonophobia plus the subject's most troublesome symptom (eg cognitive impairment, dizziness and functional disability) if other than nausea, photophobia or phonophobia. Episodes of vomiting will also be recorded.

11.5.3 Subject satisfaction

Subject satisfaction with treatment will be recorded at the end of each treatment period on a 7-point Likert scale, with 1 = very satisfied and 7 being very dissatisfied. Subjects will also be asked to record their satisfaction compared with their usual anti-migraine therapy. Subjects will be asked to complete the satisfaction survey for each Treatment period only if the dose has been taken for that period and the Treatment Preference survey only if doses have been taken in both Treatment periods.

12. Study oversight

12.1 Within-subject stopping criteria

The following criterion constitutes a contraindication to further administration of IMP to an individual subject:

- Any experience, which is considered, by the investigator and/or the sponsor to be serious, and severe and clinically significant, which would suggest significant hazard that may be associated with the use of the IMP

If the above criterion becomes applicable during the study, the subject must not receive further doses of IMP. Such subjects will be withdrawn and follow the withdrawal procedures as described in Section 5.7.

12.2 Suspension or premature termination of the study

Conditions may arise during the study that could prompt the study to be halted or the study site to be terminated. The sponsor may terminate part of, or the entire study for safety, administrative, or commercial reasons. Conditions that may prompt such considerations include, but are not limited to, the following:

- The discovery of unexpected, serious, or unacceptable risk to subjects enrolled in the study;
- A decision on the part of Sponsor to suspend, discontinue, or shorten the study;
- Study conduct at a study site may warrant termination under conditions that include the following:
 - Failure of investigator(s) to enrol eligible subjects into the study;
 - Failure of the investigator to comply with country-specific regulations;
 - Submission of false information from the research facility to the sponsor, the clinical monitor, or a regulatory authority;
 - Insufficient adherence to protocol requirements;
 - A conflict of interest of the investigator, his/her institution, or site personnel that could negatively impact the integrity of the clinical study;
 - Institution or Ethics Committee under investigation for cause.

Any decision by the sponsor on stopping or restarting the study must be discussed with the investigator. All actions are to be documented and the Ethics committee (EC) and regulatory (competent) authority notified in writing as required by local regulations. Should a protocol amendment be required, this will be managed in accordance with Section 15.1.4. The study must not recommence recruitment or dosing until approval is received in writing from the EC (if/as required by the EC).

If the study is to be terminated for safety reasons, any further administration of IMP will be stopped.

If the study is terminated for safety reasons, subjects will be followed up for a minimum of two weeks following the last exposure to IMP, at which time an End of study visit should be conducted. Refer to Section 9.6 for follow up assessments. Any AEs/SAEs ongoing at the time of the End of study visit will be followed to resolution or stabilisation (whichever is the sooner).

13. Adverse events

13.1 Definitions

13.1.1 Adverse event

An adverse event is any untoward medical occurrence in a patient or clinical investigation subject administered a pharmaceutical product and may not necessarily have a causal relationship with the administered treatment.

An AE can therefore be any unfavourable and unintended sign (including an abnormal laboratory finding), symptom, or disease temporally associated with the use of a medicinal (investigational) product, whether or not it is related to the medicinal (investigational) product. This includes an exacerbation of pre-existing conditions or events, intercurrent illnesses, drug interaction or any worsening (ie any clinically significant adverse change in frequency and/or intensity) of a pre-existing condition, which is temporally associated with the use of the sponsor's product. Anticipated fluctuations of pre-existing conditions, including the disease under study, that do not represent a clinically significant exacerbation or worsening need not be considered AEs.

Laboratory reference ranges are defined by upper or lower limits of parameters of the respective laboratory. The investigator should ensure that each parameter out of the normal range is assessed for clinical significance and the potential for being an AE (refer to Section 13.3). An adverse event is defined as 'serious' when it meets one of the pre-defined outcomes as described in Section 13.1.6.

13.1.2 Adverse drug reaction/Suspected adverse (drug) reaction

An adverse drug reaction (ADR) is any AE for which there is a reasonable possibility that the drug caused the AE. Reasonable possibility means there is evidence to suggest a causal relationship between the IMP and the adverse event.

13.1.3 Suspected unexpected serious adverse reactions

Suspected unexpected serious adverse reactions (SUSARs) are AEs that are believed to be related to an IMP and are both unexpected (ie the nature or intensity is not expected from the information provided in the Investigator's Brochure) and serious. SUSARs are subject to expedited reporting to the applicable regulatory authorities.

For regulatory reporting purposes, SUSARS will be unblinded.

13.1.4 Causality

The investigator must assign causality to each adverse event in relation to the IMP based on the following definitions:

Not related:	AE with an incompatible time relationship to IMP administration, and that could be explained by underlying disease or other drugs or is incontrovertibly not related to the Investigational Product
Possibly related:	AE with a reasonable time relationship to IMP administration, but which also could be explained by concurrent disease or other medications.
Probably related:	AE with a reasonable time relationship to IMP administration that is unlikely to be attributed to concurrent disease or other medications.
Definitely related:	AE with plausible time relationship to IMP administration and which cannot be explained by concurrent disease or concomitant medications.

13.1.5 Severity (intensity) of adverse event

Grade refers to the intensity of an AE and should not be confused with seriousness (refer Section 13.1.6).

Grade 1	Mild; asymptomatic or mild symptoms; clinical or diagnostic observations only; intervention not indicated.
Grade 2	Moderate; minimal, local or noninvasive intervention indicated; limiting age-appropriate instrumental Activities of Daily Living (ADL*).
Grade 3	Severe or medically significant but not immediately life-threatening; hospitalisation or prolongation of hospitalisation indicated; disabling; limiting self-care ADL**.
Grade 4	Life-threatening consequences; urgent intervention indicated.
Grade 5	Death related to AE.

Activities of daily living (ADL)

**Instrumental ADL – refers to preparing meals, shopping for groceries or clothes, using the telephone, managing money, etc.*

***Self-care ADL – refers to bathing, dressing and undressing, feeding self, using the toilet, taking medications, and not bedridden.*

13.1.6 Serious adverse event

A serious adverse event (SAE) is any untoward medical occurrence or effect that, at any dose:

- Results in death,
- Is life-threatening.
- Life-threatening in the definition of serious refers to an event in which the subject was at risk of death at the time of the event, it does not refer to an event which hypothetically might have caused death if it were more severe.
- Requires inpatient hospitalisation or prolongation of existing hospitalisation.
- Hospitalisation is defined as inpatient admission or care regardless of duration. Out-patient treatment in an emergency room is not in itself an SAE, although the reasons for it may be. Elective surgery, or hospital admissions and/or surgical operations planned before or during this study are not considered AEs if the illness or disease existed before the subject was enrolled in the study, provided that it did not deteriorate in an unexpected way during the study.
- Results in persistent or significant disability/incapacity.
- Is a congenital anomaly/birth defect.
- Is medically important or is a medically significant event.

Medical and scientific judgement is required to decide if prompt notification is required in situations that the investigator regards as medically important that did not strictly meet the criteria above but may have jeopardised the subject or required intervention to prevent one of the outcomes listed above, or that would suggest any significant hazard, contraindication, side effect or precaution that may be associated with the use of the IMP. Such events should also be considered as serious.

13.2 Recording of adverse events

In this study, events from Screening to prior to first dose of IMP will be captured as medical history. All

events occurring during and following the first administration of IMP will be reported as AEs or SAEs (if criteria met) until the completion of the End of study visit.

AEs that are ongoing at the End of study visit will be followed up until the event has resolved or stabilised. All followup information will be recorded in the subject's source records. All spontaneously volunteered and enquired for, as well as observed AEs, will be recorded in the subject's source records as well as the CRF.

It is preferable that AEs and SAEs be reported as diagnoses if available, rather than individual signs and symptoms. SAEs should be reported and documented in accordance with the procedures in Section 13.4. The following data should be documented for each AE: the description of the event, start and stop dates, intensity, causality and outcome must be recorded, as well as any actions taken.

13.3 Clinical lab abnormalities and other abnormal assessments

Abnormal laboratory findings (eg, clinical chemistry, haematology, and urinalysis) or other abnormal assessments (eg, ECG, vital signs) per se are not reported as AEs. However, those abnormal findings that are deemed clinically significant or are associated with signs and/or symptoms must be recorded as AEs (and recorded as an SAE if they meet the criteria of being serious) as described previously. Clinically significant abnormal laboratory or other abnormal findings that are present at baseline and worsen after first dose of IMP are to be considered AEs (and SAEs if serious).

The investigator should exercise his or her medical and scientific judgment in deciding whether an abnormal laboratory finding or other abnormal assessment is clinically significant. Usually, the abnormality should be associated with a clinically evident sign or symptom, or be likely to result in an evident sign or symptom in the near term, to be considered clinically significant. A clinically significant laboratory abnormality in the absence of clinical symptoms may jeopardize the subject and may require intervention to prevent immediate consequences.

13.4 Reporting of serious adverse events

Any SAE must be reported by the investigator if it occurs during the clinical study or within 2 weeks of the subject having received the last dose of IMP, whether or not the SAE is considered to be related to the IMP. This shall include pregnancy in a female subject or in a female partner of a male study subject. Instances of death, congenital abnormality or an event that is of such clinical concern as to influence the overall assessment of safety, if brought to the attention of the investigator at any time after cessation of IMP administration and linked by the investigator to this study, should be reported to the sponsor.

The investigator must report an SAE on an SAE report form and forward the SAE report form, the AE form and the concomitant medication form to the sponsor or delegate **within 24 hours of becoming aware of the SAE** and **regardless of causality**. All pregnancies in a female subject or in a female partner of a male study subject should be reported on a Pregnancy report form following the same reporting process and timelines required for SAEs.

The investigator should not wait to receive additional information to document fully the event before notification of a SAE, though additional information may be requested. Where applicable, information from relevant laboratory results, hospital case records and autopsy reports should be obtained.

Followup information on SAEs must also be reported by the investigational site to the sponsor within the same time frame. If a non-serious AE becomes serious, this and other relevant followup information must also be provided within 24 hours of the investigator becoming aware.

All SAEs will be recorded in the subject's source documents and the CRF.

It is the responsibility of the sponsor to determine whether a reported SAE fits the classification of a SUSAR (refer to Section 13.1.3). If the sponsor considers the SAE to be drug related (ie an adverse drug

reaction), unexpected and fulfils the criteria for a suspected unexpected serious adverse reaction (SUSAR), the sponsor has the responsibility to expedite the reporting to all concerned investigators, to the EC where required, and to the appropriate regulatory authorities within the pre-defined timelines.

The investigator must notify their EC of SAEs occurring at the site, within the time period and in accordance with requirements specified by the EC.

The sponsor and/or delegate will promptly notify all relevant investigators and the regulatory authorities of findings that could adversely affect the safety of subjects, impact on the conduct of the study or alter the ethics approval/favourable opinion of the study.

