Further details of the statistical methodology to be used in the analysis and reporting of the study results, including methods for handling missing data, and early withdrawals, will be provided in a statistical analysis plan that will be finalised prior to database lock.

Anticipated study Duration: Approximately 9 months

Participant duration: Maximum participation duration is 14 weeks (98 days): Screening (28 - 35 days), Treatment period 1 (28 days), Treatment period 2 (28 days), followup (7 days)

2. Study schedule of assessments and procedures

	Screening	Treatment period 1			End of period 1	Treatment period 2			End of period 2, early withdrawal	End of study
Visit no	1	2			3			4	5 (phone)	
Study day	-28 to -1 (+7days)	1	Telephone (if required)	Headache episode	29 ± 2 ¹	Telephone (if required)	Headache episode	57 ± 2 ¹	64 ± 2 ²	
Written informed consent	X									
Eligibility assessment	X									
Confirmation of eligibility		X								
Enrolment and randomisation		X								
Medical history, demographics	X									
Height and weight	X									
12 lead ECG	X	X			X			X		
Pregnancy test ³	X	X				X				
Vital signs	X	X			X			X		
Physical examination	X ⁴	X ⁵			X ⁵			X ⁵		
Clinical laboratory safety testing ⁶	X	X			X			X		
Concomitant medications	X	X	X	X	X	X	X	X	X	
IMP issued		X				X				
IMP administration ⁷				X			X			
Adverse event assessment			X		X	X		X	X	
Headache diary ⁸	X			X			X	X		
Migraine diary ⁹	X			X			X			
Patient satisfaction survey					X			X		

1 Or maximum 5 business days after dose of IMP

2 Or 7 days after Visit 4

3 Females of child bearing potential only, blood test at screening, urine other occasions

4 Full physical examination

5 Targeted physical examination

6 Haematology, biochemistry, urinalysis

7 Migraine episode only

8 Headache diary during both non-migraine and migraine headaches

9 Migraine diary, during migraine headaches

3. Introduction and background information

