5.7 Withdrawal of subjects from study

Subjects can terminate their participation in the study at any time, without giving a reason and without prejudice to further treatment. Subjects may also be withdrawn at any time at the discretion of the investigator(s) or sponsor for safety, behavioral or administrative reasons.

Subjects who discontinue from the study should always be asked about the reason(s) for their discontinuation and about the presence of any adverse events. The reason(s) for withdrawal will be documented in the case report form (CRF).

Possible reasons for discontinuation of a subject may include:

- Withdrawal of consent by the subject
- Serious or significant AE or laboratory abnormality
- Non-compliance with the protocol
- The need to take medication which may interfere with study measurements or is contraindicated
- New inter-current diseases, which may affect the safety of the IMP

- Subject is lost to followup
- Withdrawal for other reasons
- Lateral terminating the study for administrative, financial, or other reasons

Subjects withdrawing from the study will be requested to attend an End of study Visit. If the subject withdraws during the treatment period, the subject should attend the End of study visit within one week of the subject withdrawal, and/or a minimum 48 hours after last dose of IMP.

Any new AEs occurring during that period must also be reported in the CRF and must be followed up until resolved, unless, in the investigator's opinion, the condition is unlikely to resolve. This visit is primarily for the purposes of monitoring subject safety.

Any AEs that are continuing at the time of withdrawal from the study, should, wherever possible, be followed to resolution or stabilisation, whichever is earlier.

Reasonable efforts will be made to contact subjects who are lost to followup. These must be documented in the subject's source documents.

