Assessments including 12-lead ECG vital signs, a targeted physical examination and concomitant medications will be recorded and the subject's diaries will be reviewed. Blood and urine samples will be taken for safety monitoring and pregnancy testing (FOCBP). Subject satisfaction with Treatment Period 1 IMP will be recorded (if dose taken). Results from safety monitoring tests are not required prior to dosing.

Treatment period 2

Subjects will leave the clinic with their diaries and one dose of IMP (alternate treatment), to take the dose within one hour of the onset of a migraine of moderate to severe intensity (NRS ≥ 4), but not less than 48 hours after last dose, and instructions to complete the diaries as for Treatment period 1. No analgesics or antimigraine medication other than medications for routine prophylaxis not on the Prohibited medicines list may be taken within 24 hours prior to taking the dose of IMP. Rescue medication is permitted a minimum of 2 hours post dose.

The subject's symptoms including, nausea, photophobia and phonophobia plus the subject's most troublesome symptom if other than nausea, photophobia or phonophobia will be recorded at the time of dosing and at 0.5, 1.0, 1.5, 2, 4, 8 and 24 hours after taking the dose. Episodes of vomiting will also be recorded

The subject will be instructed to phone the clinic within 24 hours (or one business day) of taking the second dose.

If the subject has not phoned the clinic, the subject will be phoned 14 days after Visit 3 to remind them to complete their diaries, and to phone the clinic when the dose has been taken.

Subjects will return to the clinic for Visit 4 within 5 business days after taking the dose or a maximum of 28 days after Visit 3.

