9.6 End of study (Visit 5)

Subjects will be phoned one week after Visit 4 to review any new or changed adverse events or changes in concomitant medications.

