9.7 Early withdrawal visit

An early withdrawal visit should be conducted within one week of the subject withdrawal, and/or a minimum 48 hours after last dose of IMP.

Subjects who are completing an early withdrawal visit will return with their diaries and unused IMP.

Blood and urine samples will be taken for safety analysis. 12-lead ECG, vital signs, concomitant medications, targeted physical examination results and adverse events will be recorded. Subjects will be asked to complete assessments for subject satisfaction.

10. Study endpoints

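### For subjects dosed in period 2, the closing call falls on day 8 to 14 after the dose, so up to 6 days of the two-week SAE window may pass without active enquiry

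*Protocol*

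**What the plan says.** Protocol 13.4 obliges the investigator to report any SAE "if it occurs during the clinical study or within 2 weeks of the subject having received the last dose of IMP", whatever the causality.

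The visit timing that decides when the site last asks about events is elsewhere. In the treatment period 2 text of Protocol 9.4, "Subjects will return to the clinic for Visit 4 within 5 business days after taking the dose". Protocol 9.6 then gives the closing contact: "Subjects will be phoned one week after Visit 4 to review any new or changed adverse events". Footnote 2 of the schedule (Protocol 2 and SAP 5) gives the same seven-day interval. No later contact is scheduled.

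Protocol 13.2 says that events after the first dose "will be reported as AEs or SAEs (if criteria met) until the completion of the End of study visit". The same section adds that "SAEs should be reported and documented in accordance with the procedures in Section 13.4".

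For early withdrawal, Protocol 5.7 asks the subject to "attend the End of study visit within one week of the subject withdrawal, and/or a minimum 48 hours after last dose", and Protocol 9.7 gives the same timing for what it calls an early withdrawal visit. SAP 10.3 maps early termination to Visit 5 (End of Study). The schedule instead places early withdrawal in the Visit 4 column, headed "End of period 2, early withdrawal".

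**The concern.** The protocol sets a two-week window for SAEs but does not time its last enquiry to reach the end of that window. Protocol 11.3 has AEs elicited by direct questioning at each visit. Once the closing call has been made, a new SAE reaches the site only if the subject or someone else raises it.

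The two end points add to this. Whenever the call comes before day 14, the stop point in 13.2 is earlier than the limit in 13.4, and a site working from 13.2 could take the period as closed.

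At stake is the completeness of safety capture for new-onset SAEs in a few late days, in the first study of LAT8881 in migraine. SAP 10.10 sets no end date for treatment-emergent events, so the tables would include such an event if it were collected. No efficacy analysis is affected.

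**Working it through.** **The plan's own timeline.** Maximum participation in Protocol 5.6: 35 + 28 + 28 + 7 = 98 days. Visit 5 in the schedule: day 57 + 7 = day 64. Both reproduce.

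**Inputs.** SAE window: 14 days after the last dose (13.4). Visit 4: business day 1 to 5 after the period 2 dose (9.4). Call: Visit 4 + 7 days (9.6). Assumptions: Visit 4 is on the first business day after the dose at the earliest, there are no public holidays, and no ±2-day tolerance applies.

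**Formulas.** Let k be the number of calendar days from dose to Visit 4. Call day = k + 7. Gap = 14 − (k + 7) = 7 − k.

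**Values of k by dosing weekday, for business days 1, 2, 3, 4, 5.** Mon 1, 2, 3, 4, 7. Tue 1, 2, 3, 6, 7. Wed 1, 2, 5, 6, 7. Thu 1, 4, 5, 6, 7. Fri 3, 4, 5, 6, 7. Sat 2, 3, 4, 5, 6. Sun 1, 2, 3, 4, 5.

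**Gap in days (7 − k).**

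| Visit 4 on business day | Mon | Tue | Wed | Thu | Fri | Sat | Sun | Range |
|---|---|---|---|---|---|---|---|---|
| 1 | 6 | 6 | 6 | 6 | 4 | 5 | 6 | 4–6 |
| 2 | 5 | 5 | 5 | 3 | 3 | 4 | 5 | 3–5 |
| 3 | 4 | 4 | 2 | 2 | 2 | 3 | 4 | 2–4 |
| 4 | 3 | 1 | 1 | 1 | 1 | 2 | 3 | 1–3 |
| 5 | 0 | 0 | 0 | 0 | 0 | 1 | 2 | 0–2 |

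k runs from 1 to 7, so the call is on day 8 to 14 and the gap is 0 to 6 days. The call reaches day 14 only when Visit 4 is on business day 5 after a Monday-to-Friday dose. From business day 2 onward the gap is 0 to 5 days.

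**Sensitivity.** If the schedule's ±2 days also applies to the call, the call is on day 6 to 16 and the gap is 0 to 8 days.

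**Subjects dosed only in period 1** who stay in the study have their closing call well past day 14, so they are not affected.

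**Early withdrawals.** If the visit is 48 hours after the dose and no call follows, the gap is 14 − 2 = 12 days. If a call follows 7 days later, it is on day 9 and the gap is 14 − 9 = 5 days.

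**Participation after the fix.** If 28 days caps Visit 4 (the 9.4 wording), a dose on day 27 with Visit 4 on day 28 puts the call on day 27 + 14 = 41, so 35 + 28 + 41 = 104. A dose and Visit 4 both on day 28 give 35 + 28 + 42 = 105. The synopsis applies the 28-day limit only when IMP has not been taken. On that reading a day-28 dose may be followed by a visit up to 7 calendar days later in each period. The maximum is then already 35 + 35 + 35 + 7 = 112, and the fix leaves it there, because 28 + 14 = 35 + 7 = 42.

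**The case against.** A reporting window is not a contact window. Section 13.4 binds the investigator, and nothing in the protocol says that every day of the window needs an active question. Section 13.2 sends SAEs to 13.4, so a site would have to overlook that cross-reference to stop early. Section 13.4 also covers deaths and events of major concern at any later time if the investigator hears of them and links them to the study, and 13.5 keeps open events under follow-up. The 6-day figure needs Visit 4 on business day 1, when the 24-hour diary entry may be barely complete. These are single doses of a compound already given to over 700 subjects.

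Most of this stands. A reader might infer that SAEs after the call go unreported by design; the cross-reference and 13.4 itself rule that out. A reader might also take the table as a frequency, or 6 days as typical; the documents do not say when Visit 4 is booked, so neither follows. Nor can it be said that subjects are not told to report later events, because the consent material is not in the documents available. For early withdrawals, it would be too strong to say the text gives no answer: Protocol 5.7 and SAP 10.3 agree that the visit is the End of study visit. Only the schedule column points the other way, and the agreed reading is the one under which no call follows.

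What remains is a difference in stated end points and a last enquiry that usually need not reach day 14. Section 12.2 supports closing it: if the study is terminated for safety, it requires at least two weeks of follow-up after the last exposure before the End of study visit.

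**Conclusion.** The point holds as a minor gap in active enquiry and wording. For subjects dosed in period 2, 0 to 6 days of the protocol's own SAE window may have no scheduled enquiry, falling to 0 to 2 days if Visit 4 is on business day 5. Dosed early withdrawals could have up to 12 days if no call follows a visit at 48 hours. These figures rest on nominal timing and on Visit 4 no sooner than the next business day. Exposure is limited: about 20 completers, single doses and new-onset events only. The priority is low, but the change is cheap enough to be worth making.

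**What to change.** - In Protocol 9.6, schedule footnote 2, the synopsis and SAP 5, time the Visit 5 call at the later of 7 days after Visit 4 and 14 days after the last IMP dose.
- In Protocol 5.7 and 9.7, give dosed early withdrawals a call on or after day 14.
- In Protocol 13.2, end SAE reporting at the later of the End of study contact and 14 days after the last dose, so that it matches 13.4.
- In the same amendment, bring the End of study timing in Protocol 5.1 and SAP 4.1 (currently within 7 days of the period 2 treatment) into line with 9.6, and restate maximum participation in 5.6 and the synopsis.

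Cost: the existing call moves up to about 6 days later for some subjects, and dosed early withdrawals get one extra call. Maximum participation rises from 98 to about 104 or 105 days on the capped reading and does not change on the other. The wording touches several sections and goes through a routine amendment with ethics committee review. Any change to the participant information needs approval before use (Protocol 15.1.4). Changing 13.2 alone would remove the mismatch in wording but not the gap in enquiry.
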